A total of 36 individuals will be recruited for this study, 18 in each group. Approximately 60% in each group will be female. The primary outcome measure of this study is the change in absolute FPA performance error (the difference between the performed and the targeted FPA), which is indicative of how ‘accurate’ the patient is when performing the modification. This outcome measure is only relevant to the SMOD group, who have a specific target for their modification; therefore, allowing an error value to be calculated. This outcome will be measured during immediate and delayed retention at week one compared to follow-up and will provide evidence of the extent to which motor learning has occurred. Previous FPA performance error during immediate retention testing after a six-week FPA modification resulted in a small effect (Cohens $d = 0.35$) [3]. We are also interested in exploring the clinical and biomechanical differences between the SMOD and AMAC gait modification groups; however, no study has previously compared these methods of gait modification. Therefore, we will be conservative and base our sample size calculation on the between-within interaction effect of a 2×4 (group = 2: SMOD vs AMAC; measure = 4: immediate and delayed retention tests at week 1 and follow up) repeated measures ANOVA with an effect size of $f = 0.175$ ($f = d / 2$). With power = 0.8 and alpha = 0.05, a total sample of 30 is required [4]. With a conservatively estimated attrition of 15%, we will recruit 36 participants total (18 per group).

Procedures

Recruitment and screening

Volunteers will be recruited via print and social media, and via our database of previous participants who have indicated interest in participating in future studies. Interested volunteers will be screened via phone, email, or our lab website by the study coordinator to assess inclusion and exclusion criteria. Those deemed preliminarily eligible will be invited to attend a gait screening appointment. Eligible participants who pass the gait screen will be referred for a radiographic assessment of their knees to confirm the presence of structural signs of knee OA.

Standing, semi-flexed posteroanterior radiographs of both knees will be taken. A trained assessor will grade all radiographs based on the KL criteria. Those passing all screening requirements will be invited to enroll in the study.

Gait screening

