directly in front of the treadmill. The SMOD group will be guided to increase their FPA by 15° in either the toe-in or toe-out direction (determined by the gait screen). A line of tape will be aligned on the mirror according to the target FPA, as we have done previously [5, 17]. This mirror-based method of providing a target for the FPA modification was shown to be similarly effective when compared to feedback delivered using an expensive real-time motion capture system, but with significantly greater clinical feasibility. The AMAC group will be instructed to increase their FPA by “as much as is comfortable”. The mirror will be provided during practice sessions; however, no tapeline will be placed. The amount of time spent with the feedback (mirror) visible will be progressively reduced (faded feedback) across the six weekly practice sessions in order to reduce the reliance on feedback [18]. Before and immediately after the practice sessions, the participant will perform a warm-up and cool-down walk while wearing the sensorized shoes (10-minute outdoor standardized walking loop). This will provide a repeatable non-laboratory-based measure of FPA. Both groups will be encouraged to practice their gait modification at any opportunity during their daily at-home walking. Practice sessions will be led by a kinesiologist with experience delivering gait modification interventions.

Learning will be measured during 1) practice, 2) immediate and delayed retention tests, 3) dual-task tests, 4) transfer tests, and 5) during at-home/community walking. Each test (2-4) will last 1 min and be collected at each practice session. For the SMOD group, the absolute performance error (absolute error = |performed FPA – target FPA|), FPA variability, and the proportion of steps with >7° of change from baseline FPA will be measured using the sensorized shoe. For the AMAC group, FPA variability and the proportion of steps with >7° of change from baseline FPA will be measured. Retention tests will occur immediately before (starting at practice session 2) and after practice bouts. The participant will be asked to perform their gait modification as accurately as possible for 1 minute. Dual-task testing will be performed identically to the baseline assessment described above; however, the participant will be asked to simultaneously perform their gait modification. Lastly, transfer testing will be performed during stair ascent and descent in the same manner as the baseline assessment.

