Official Title: Foot progression angle modification: an exploratory six-week intervention in people with knee osteoarthritis.

NCT Number: TBD

Document Date: Mar 24th, 2020

Statistical Analysis Plan

Statistical analyses will be performed by an independent statistician. Means and standard deviations will be calculated for each outcome measure and baseline demographic characteristic. Baseline demographic data (e.g. age, body mass index, disease severity) will be examined for between-group differences using unpaired two-tailed t-tests. For all statistical analyses, alpha will be set to 0.05. Any multiple pairwise comparisons will be adjusted using the Bonferroni correction method.

Data will be assessed for sphericity, homoscedasticity, and normality using Mauchley's test, residual versus predicted plots, and quantile-quantile plots. Homoscedasticity and normality assumptions will be confirmed using Levene's test and Shapiro-Wilk's test, respectively. Sphericity assumption violations will be corrected for using the Greenhouse Geisser approach. Violations of homoscedasticity will be corrected for by bootstrapped model parameters. If normality is not met, a non-parametric test will be used.

Primary Hypotheses:

Repeated measures analyses of variance (ANOVA) will be performed to examine the within-group changes in learning outcomes over the six-week intervention. Between-group differences will be examined using a two-way mixed ANOVA, with the repeated measure being the learning outcome (foot progression angle change from baseline during in-lab and at-home walking) and the between-subject factor being group assignment (SMOD vs AMAC).

Secondary Hypotheses:

Biomechanical (knee joint moments), clinical (NRS knee pain, KOOS pain, symptoms, and physical function scores), and difficulty (difficulty of performing the FPA modification) change scores will be examined using an analysis of covariance (ANCOVA) with significant between-group baseline demographic group differences and baseline outcome values included as covariates.

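### The SAP's primary ANOVAs normally drop anyone with an incomplete set of sessions and carry no missing-data rule; a linear mixed model with a suitable covariance would use every recorded session

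*SAP*

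**What the plan says.** The SAP, under Primary Hypotheses, gives the within-group method: "Repeated measures analyses of variance (ANOVA) will be performed to examine the within-group changes in learning outcomes over the six-week intervention". Between-group differences go to a two-way mixed ANOVA. The preceding paragraph plans a Mauchly test and a Greenhouse-Geisser correction, so the classical form is meant. It also covers homoscedasticity and normality. The SAP contains no analysis set, missing-data rule, imputation or mixed model.

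The protocol, under Participants, derives the sample size: "With power = 0.8 and alpha = 0.05, a total sample of 30 is required". The model is a group-by-measure interaction with effect size f = 0.175 and "measure = 4: immediate and delayed retention tests at week 1 and follow up". Then: "With a conservatively estimated attrition of 15%, we will recruit 36 participants total (18 per group". Attrition is the only loss allowed for.

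Under Gait modification intervention there are six weekly sessions, with one-minute retention, dual-task and transfer tests. The pre-practice test has one value fewer than the post-practice test: "Retention tests will occur immediately before (starting at practice session 2) and after practice bouts". FPA is logged by a custom shoe sensor, and the SAP's repeated measure also takes in walking at home.

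**The concern.** A classical repeated-measures ANOVA needs a value in every cell for each participant. Without another rule, standard software removes the whole participant when one value is absent. A person who misses session 4, or whose shoe fails to log that day, then contributes nothing. A person who leaves at week 5 loses the four sessions already recorded.

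The design offers many openings for such gaps: six visits, several tests per visit, a sensor writing to a memory card, and home walking that is requested rather than supervised. The exclusion of people unable to attend every appointment limits missed visits, but not device failures or unrecorded walking.

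Two things are at stake. One is precision in arms of 18. The other is the assumption about missingness: complete-case ANOVA is valid in general only if data are missing completely at random, and nothing in the plan supports that. With no rule written down, the statistician would also have to choose one after seeing the data.

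**Working it through.** **1. The plan's own figure.** Inputs from the protocol: f = 0.175, k = 2 groups, m = 4 measures, alpha 0.05, power 0.80. The correlation between measures (rho) is not given; sphericity is assumed. The formula is lambda = f² × N × m / (1 − rho), with df1 = (k − 1)(m − 1) = 3 and df2 = (N − k)(m − 1).

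- rho = 0.5 gives N = 46, and power at N = 30 is 59%.
- rho = 0.68 to 0.70 gives N = 30, with power 80% to 83%.

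So 30 is reproducible only with an unreported correlation near 0.7. The attrition step does reproduce: 30 / 0.85 = 35.3, rounded up to 36. In reverse, 36 × 0.85 = 30.6. If the planned attrition occurs, almost nothing is left for gaps among those who stay.

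**2. Complete records in one arm.** Let q be the chance that a session value is missing, assumed independent across sessions. Expected complete six-session records are 18 × 0.85 × (1 − q)^6, where 18 × 0.85 = 15.3:

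- q = 3%: 15.3 × 0.833 = 12.7
- q = 5%: 15.3 × 0.735 = 11.2
- q = 10%: 15.3 × 0.531 = 8.1

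**3. Power in one arm.** Simulation, 3,000 trials per setting: n = 18, six sessions, equal correlation 0.7, 15% monotone dropout, independent gaps at rate q, and a linear change reaching 0.6 SD at the last session. The comparison is the complete-case ANOVA F test against a within-person F test on all available sessions.

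| Gaps per session | Complete-case | All sessions |
|---|---|---|
| 0% (dropout only) | 0.76 | 0.78 |
| 3% | 0.66 | 0.75 |
| 5% | 0.60 | 0.74 |
| 10% | 0.42 | 0.72 |

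Type I error was about 5% for both. Repeat runs agreed within about 0.02.

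**4. The 2×4 model that was sized.** With 30 retained and rho = 0.68, power with complete data is 80.2%. Complete cases number 30 × (1 − q)^4. The second power figure uses generalised least squares on all available data.

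- q = 2%: about 28 complete; 76% against 79%
- q = 5%: about 24 complete; 69% against 77%
- q = 10%: about 20 complete; 58% against 73%

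The loss is smaller than over six sessions, and using all data recovers most of it, not all.

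**5. Does any mixed model do?** No. Complete data were simulated with no true change, n = 18, six sessions, and correlation decaying over time (AR(1), 0.7 to 0.8, assumed). The week 1 to week 6 contrast from a model equivalent to a random intercept rejected about 12% to 14% of the time at nominal 5%. The uncorrected omnibus F rejected about 8%, and the Greenhouse-Geisser version about 4%. A random intercept on its own would thus give up protection that the SAP now has.

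**The case against.** **The link to N = 30.** A reader might infer that missed sessions use up the 30 on which the plan relies. The documents do not support that. The 30 belongs to a 2×4 retention-test model, and if week 1 is read as sessions 1 and 2, a gap in sessions 3 to 6 removes nobody from it. Dropouts are already inside the 15%. If nobody drops out, 36 × 0.97^6 = 30.0, so the spare six absorb about 3% missing per session.

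**Listwise deletion is inferred.** Neither document states it. Nor does the SAP list the levels of the time factor, and H1 and H2 (week 1 to week 6) could be met by a two-occasion comparison, which would lose fewer people. This stands, but it is also why the rule needs writing down.

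**The rate is assumed.** The documents give none, and the attendance criterion together with an attrition figure described as conservative point to a low one. Gaps that cluster within people would leave more complete records at the same rate. This stands; the range shows the sensitivity and is not a forecast.

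**Upward bias.** It is tempting to say that full attenders learn better, so the learning curve is inflated. That is plausible, but nothing in the documents shows it, and gaps unrelated to outcome, as simulated, cannot show it.

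**The simulation is not the recommended model.** Its all-session test assumes equal correlations, which held in the simulated data. An unstructured covariance over six sessions has 6 × 7 / 2 = 21 parameters to estimate from 18 people in one arm and would recover somewhat less. This stands.

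**Conclusion.** The point holds in a limited form. The SAP names methods that normally need complete rows, gives no missing-data rule, and recruits with an allowance for attrition alone. A mixed model on all recorded sessions is a better choice at small cost.

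The size depends on an unreported gap rate. Under the assumptions above, one arm loses about 0.09 of power at 3% gaps (0.75 − 0.66), 0.14 at 5% (0.74 − 0.60) and 0.30 at 10% (0.72 − 0.42). With dropout alone the difference is about 0.02, and the case then rests on the weaker missing-data assumption rather than on power. The plan should act on this, but the documents do not show that the trial is underpowered because of it or that its estimates would be biased.

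**What to change.** Replace the repeated-measures and mixed ANOVAs for the learning outcomes with a linear mixed model fitted by REML to every recorded session.

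- **Fixed effects:** session as a categorical factor. For outcomes measured in both groups (FPA variability, proportion of steps beyond 7°, FPA change), add group and group-by-session. Fit absolute FPA error in SMOD only, without group terms, because AMAC has no target.
- **Covariance:** unstructured with Kenward-Roger degrees of freedom, and a prespecified fallback, such as heterogeneous AR(1) or Toeplitz, if it does not converge. Do not rely on a random intercept alone. The Mauchly and Greenhouse-Geisser steps can be dropped only once such a covariance is in place.
- **Contrasts:** week 1 to week 6 for H1 and H2; week 1 to follow-up for the retention tests. State that the pre-practice test has no session 1 value and which session stands for its week 1.
- **Missing data:** state the missing-at-random assumption, and say what makes a session value missing (missed visit, sensor failure, no home recording).

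The cost is SAP wording and slightly more programming. The analysis will rely on missing at random, which is weaker than the missing-completely-at-random assumption of a complete-case ANOVA but still cannot be tested from the data.

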Official Title: Foot progression angle modification: an exploratory six-week intervention in people with knee osteoarthritis.

NCT Number: TBD

Document Date: March 24th, 2020

Study Protocol

Study Design

This parallel-group randomized clinical trial will consist of a 6-week gait modification intervention, delivered to two groups of older adults with medial compartment knee osteoarthritis (OA). The first group will receive a conventional delivery of gait modification (group name: SMOD), whereby they will practice the gait modification with a specific target (rotate foot 15° inward or outward relative to baseline). The second group will self-select the amount of modification they perform (group name: AMAC), guided by the instruction to “change foot rotation as much as is comfortable”. Foot rotation (toe-in or toe-out walking) is measured during the stance phase of walking as the angle of the foot’s long axis (heel to toe) relative to the direction of walking, and termed foot progression angle (FPA). In-lab and real-world gait analysis will be used to examine how the modification is learned, as well as the effect of the modification on biomechanical and clinical outcomes relevant to knee OA. In-lab assessment will be performed at baseline and a 7 week follow-up, while real-world assessment will be performed during the intervening weeks using wearable sensor technology (a custom sensorized shoe design). Both within-group and between-group comparisons will be made to identify differences in learning, difficulty, biomechanical, and clinical outcomes.

Primary Hypotheses

- H1: Participants receiving the specific FPA target will exhibit improved learning outcomes (e.g. lower error in performance, higher proportion of steps with $\geq 7^\circ$ of change from baseline FPA and lower variability) from week 1 to week 6, as measured during gait modification practice sessions, learning assessments, and during daily walking activity.
- H2: Participants receiving the self-directed FPA modification will exhibit improved learning outcomes (higher proportion of steps with $\geq 7^\circ$ of change from baseline FPA and lower variability) from week 1 to week 6, as measured during gait modification practice sessions, learning assessments, and during daily walking activity.
- H3: We expect FPA variability will be larger in the self-directed group, but both groups will exhibit a similar proportion of steps with $> 7^\circ$ of change from baseline FPA.

Secondary Hypotheses

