Questionnaires will be administered which will include an 11-point numerical rating scale (NRS) depicting average knee pain over the previous week where 0 = “no pain”, 10 = “worst pain imaginable”, the Knee Injury and Osteoarthritis Outcome Score (KOOS) [8], and the Pain Catastrophizing Scale [9]. Medical history, anthropometrics (height, body mass etc.), age, and symptom duration will also be recorded by the assessor. The timed stair climb (a measure of physical function) will be performed on a 12-stair flight. Participants will be instructed to “climb as quickly, but safely as possible” [10]. Two repetitions will be performed, and the fastest time will be used.

B) Gait analysis

A total of 52 reflective markers (45 lower limbs; 7 upper limbs) will be affixed to the skin bilaterally over key anatomical landmarks as is standard in our laboratory [11]. Fourteen high-

speed cameras (sample rate = 100 Hz) will track the positions of these markers and two floor-embedded force platforms (sample rate = 2000 Hz) will measure ground reaction forces. Five passes along a 10m instrumented walkway will be performed barefoot and then shod. Walking speed at the baseline assessment will be measured using two timing gates placed at a known distance along the walkway. At follow-up, participants will first complete five walking passes at a self-selected speed and then be constrained to walk within $\pm 5\%$ of their baseline walking speed, due to the impact of walking speed on joint moments. After over-ground walking, a 5-minute treadmill walk will be performed while wearing a pair of sensorized shoes (details included below). This will provide a controlled measurement of FPA from the sensorized shoe for comparison with FPA measured at each practice session and during daily at-home walking.

A 1-minute dual-task assessment will be performed immediately after the 5-minute treadmill walking trial, according to established methods [12]. Briefly, a single letter or category will be provided at the start of the 1-minute period. The instructions will be to continue walking naturally while simultaneously dictating as many words as possible (word-list generation) that start with the letter or belong to the category. The number of correct words dictated will be recorded.

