Stair ascent and descent will be performed while wearing the sensorized shoes. This will take place at a building nearby the laboratory (5-minute walk) because of the availability of continuous linear sets of stairs for multiple flights. This allows the use of the sensorized shoe for measuring FPA during stair ascent and descent. These FPA data will be compared with transfer test data (details included below) examined at several points throughout the intervention. These same shoes will be provided to the participant to measure real-world FPA during at-home and community walking.

Sensorized shoes

A custom inertial sensor consisting of a 3-axis accelerometer (signal range: $\pm 4g$), gyroscope ($\pm 500^\circ/s$), and magnetometer ($\pm 1200\mu T$), sampling data at 100 Hz will be embedded in the sole of the shoe. A previously published custom sensor fusion algorithm [13], programmed into a microcontroller, calculates the FPA in real time and stores it on a microSD card for later extraction. The sensorized shoe design and algorithm has been validated during treadmill [14] and over-ground walking [15] with excellent validity and reliability (absolute error = 1.7° and intraclass correlation coefficients > 0.9).

Randomization

Once deemed eligible and baseline data collection is complete, each participant will be randomized to either the SMOD or AMAC group. Randomization will be performed using an *a priori* block-stratified approach based on sex and KL grade. A predetermined randomization matrix will be computed [16] by a team member not involved in testing or the intervention. Group allocations will be stored in opaque envelopes, which will be opened in a sequential manner after baseline testing and before the first practice session. The group allocation will be communicated to the study trainer via email.

Gait modification intervention

Both groups will attend six practice sessions conducted weekly, which will last approximately 1 hour each. Walking practice will be conducted on a treadmill with a full-length mirror placed

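### The primary between-group mixed ANOVA has no baseline covariate, although sensorized-shoe FPA is recorded before randomisation; adding one gains precision on the group main effect, chiefly for FPA variability in H3

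*SAP*

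**What the plan says.** SAP, Primary Hypotheses: "Between-group differences will be examined using a two-way mixed ANOVA, with the repeated measure being the learning outcome". The sentence goes on to define that outcome and the only between-subject term: "foot progression angle change from baseline during in-lab and at-home walking) and the between-subject factor being group assignment (SMOD vs AMAC". No covariate is named.

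SAP, Secondary Hypotheses: change scores are analysed by ANCOVA, with "baseline outcome values included as covariates".

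Protocol, Primary Hypotheses, H3: "We expect FPA variability will be larger in the self-directed group, but both groups will exhibit a similar proportion of steps" (those more than 7° from baseline FPA).

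Protocol, Baseline and follow-up data collection, B) Gait analysis: "a 5-minute treadmill walk will be performed while wearing a pair of sensorized shoes". Its purpose is stated: "This will provide a controlled measurement of FPA from the sensorized shoe for comparison with FPA measured at each practice session".

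Protocol, Randomization: "Once deemed eligible and baseline data collection is complete, each participant will be randomized to either the SMOD or AMAC group". Stratification is by sex and KL grade.

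Protocol, Gait modification intervention: the learning outcomes come from the same instrument. For SMOD, error, variability and the proportion beyond 7° "of change from baseline FPA will be measured using the sensorized shoe"; for AMAC, the last two are measured.

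**The concern.** A measurement of natural gait is taken with the outcome instrument before allocation, and the primary between-arm model does not use it as a covariate. The SAP applies that method to the secondary outcomes and gives no reason for leaving it out here.

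The consequence differs by outcome:

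- **FPA variability** is the one directional between-arm prediction in H3. It is not referenced to baseline, so a person's natural step-to-step variability is not used at all.
- **FPA change** uses baseline by subtraction, which fixes the baseline coefficient at 1 instead of estimating it.
- **The proportion of steps beyond 7°** uses baseline only to set each person's threshold.

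In a trial planned for about 15 completers per arm, and not stratified on FPA, explainable variance then stays in the error term, and a chance baseline difference can move the single estimate that the trial produces.

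**Working it through.** **The plan's own figure.** Protocol, Participants gives f = 0.175, power 0.80, alpha 0.05, 2 groups, 4 measures and N = 30 for the group × measure interaction. The correlation among measures, ρ, is not stated. With λ = N·f²·m/(1 − ρ) and df = 3 and 3(N − 2), N = 30 is returned for ρ of about 0.68 to 0.70. At ρ = 0.70, λ = 30 × 0.030625 × 4/0.30 = 12.25 and power is 0.83; at ρ = 0.68, power is 0.80. Attrition: 30/0.85 = 35.3, so 36. I use 15 completers per arm below.

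**Which test is affected.** A covariate that enters as a main effect is constant across a person's tests, so it drops out of the within-person contrasts that form the interaction. Subtracting one baseline value from every test drops out in the same way. Only the group main effect gains. H3's variability prediction is about level between arms, so that is the relevant term.

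**Variance at one time point.** Assume equal SD (set to 1) at baseline and outcome, with correlation r:

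- raw outcome: 1
- change score: 2(1 − r)
- baseline covariate: 1 − r²

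The saving against a raw outcome is r². The saving against a change score is 1 − (1 − r²)/[2(1 − r)] = (1 − r)/2.

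| r (assumed) | saving vs raw (variability) | saving vs change score (mean FPA) |
|---|---|---|
| 0.1 | 1% | 45% |
| 0.3 | 9% | 35% |
| 0.5 | 25% | 25% |
| 0.7 | 49% | 15% |

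The two columns run in opposite directions, so a figure for one outcome must not be carried over to the other.

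**Power for variability.** Noncentral F with λ = 15·d²/[2(1 − r²)], df 28 unadjusted and 27 adjusted. The between-arm difference d is an assumption. The protocol's d = 0.35 comes from a performance-error result, so applying it to variability is an assumption too.

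| d (SD) | unadjusted | r = 0.1 | 0.3 | 0.5 | 0.7 |
|---|---|---|---|---|---|
| 0.80 | 56% | 56% | 60% | 68% | 84% |
| 0.35 | 15% | 15% | 16% | 19% | 25% |

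**Averaging four tests.** Take the mean of four tests that correlate 0.7 with each other, and write rb for the correlation of baseline with each test. The variances are (1 + 3 × 0.7)/4 = 0.775 raw, 0.775 + 1 − 2rb for a change score, and 0.775 − rb² with the covariate. For rb = 0.1/0.3/0.5/0.7 the covariate saves 1/12/32/63% against raw and 51/42/32/24% against change. The pattern is the same. Simulated power at 0.8 SD (raw / change / covariate) is 0.68/0.50/0.71 at rb = 0.3, 0.67/0.67/0.82 at 0.5 and 0.66/0.93/0.97 at 0.7.

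**Chance imbalance.** With 15 per arm the baseline difference has SD √(2/15) = 0.37 SD, and it exceeds 0.5 SD in either direction with probability 17%. A 0.5 SD imbalance shifts a raw outcome by 0.5r (0.25 SD at r = 0.5) and a change score by −0.5(1 − r) (−0.35 SD at r = 0.3).

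**Type I error.** Simulated with no true effect at rb = 0.5: 0.050 raw, 0.049 change, 0.051 covariate.

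**The case against.** The strongest reply is that the SAP's named outcome is already change from baseline, and that the 7° proportion is defined against each person's own baseline FPA. A reader who stops at the model name might infer that the comparison ignores baseline and that natural toe angle passes straight into H3. The SAP does not support that reading. For those two outcomes the issue is subtraction or thresholding versus a fitted covariate, which is a question of efficiency. This stands, and it limits the full point to variability.

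Other limits also stand:

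- Natural gait may predict a newly learned gait poorly, and nothing in the documents gives r. At r = 0.1 the gain for variability is nil for practical purposes.
- At 0.35 SD, power stays low whatever r in the range is taken.
- A reader might infer that imbalance invalidates the test, or that the test the trial was sized on would gain. Neither follows: type I error holds, and the interaction is unchanged.
- The declared primary outcome is absolute error in SMOD only, and H1 and H2 are within-group. Only H3 is touched, in a trial titled exploratory.
- Baseline FPA variability is not listed as a measure; it has to be derived from the treadmill record. No at-home shoe walk before randomisation is described, so an exactly matched baseline does not exist for at-home outcomes.

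None of this gives a reason to leave the baseline measurement out. The covariate had the highest power of the three options at each simulated correlation, and the data are already to be collected.

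**Conclusion.** The point holds as a modest, inexpensive improvement in precision for H3. It applies in full to FPA variability, and as change score versus ANCOVA to mean FPA. For the 7° proportion the same reasoning favours natural mean FPA as covariate, but I have not quantified that gain.

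The size is conditional on r. For variability it ranges from nothing useful at r = 0.1 to about half the variance at r = 0.7; for mean FPA it ranges from 45% down to 15%. These figures assume equal SDs at baseline and outcome, 15 completers per arm, and that H3's outcomes go through the stated mixed ANOVA, since the SAP names only FPA change there.

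A covariate does not by itself establish H3's similar proportion: the plan gives no equivalence margin, and a non-significant difference would not show similarity.

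**What to change.** In the SAP, Primary Hypotheses, name FPA variability and the proportion of steps beyond 7° as outcomes of the between-group model. Then add one pre-randomisation covariate from the baseline shoe treadmill walk:

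- natural FPA SD when the outcome is variability;
- natural mean FPA, signed toward the person's assigned toe-in or toe-out direction, when the outcome is FPA change or the proportion beyond 7°. That direction is set at the gait screen, so the signed value also precedes randomisation.

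Use the treadmill value for at-home outcomes as well. List baseline FPA SD as a derived baseline measure, and fix the choice before any unblinded analysis.

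The cost is a few lines in the SAP, one degree of freedom (28 to 27 with 15 per arm) and no new data. If r turns out near 0.1, little is gained for variability and almost nothing is lost.
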